Administrative offices for the division are located in the Fahey Building on the LUMC campus where office furniture, file cabinets, and use of essential equipment (e.g., copier, fax, phone, computer) will be provided.

V. Study Design

a. Experimental design of the study:

This is a non-randomized observational study designed to provide preliminary data on the feasibility and effectiveness of a self-administered HYP treatment for FD.

b. Study population general description

Eligible patients will be referred by Gastroenterologists within the Digestive Health Program at Loyola University Medical Center and will have received a diagnosis of functional dyspepsia. Additionally, any patients with functional dyspepsia referred by outside providers to [name] GI Behavioral Medicine Service at LUMC will be made aware of the study.

c. Sample size determination and power analyses

We will enroll 23 adults with FD from the Loyola University Medical Center outpatient gastroenterology practices, with the aim of assessing feasibility and acceptability of HYP treatment using on-line audio recordings. Sample size was determined for aim 1 of the study. Allowing for up to 20% drop-out and having at least 16 patients complete the study through the end of treatment (where the primary endpoint will be measured) will provide sufficient participant feedback on the web interface as well as the pilot data needed to power a future randomized controlled trial.

d. Study outcomes/endpoints

The primary endpoint for this study will be FD symptom scores. Secondary endpoints will be disease-specific quality of life, psychological indices, and patient satisfaction.

VI. Study Procedures

a. Subject selection procedures:

We will enroll 23 adults with FD.

Inclusion criteria

- (1) Diagnosis of functional dyspepsia by a gastroenterologist
- (2) Meeting ROME IV diagnostic criteria for functional dyspepsia
- (3) At least 18 yrs of age (no upper age limit)
- (4) Able to give informed consent
- (5) English speaking
- (6) Have daily personal access to the Internet via laptop or desktop computer, tablet or a smartphone.

Exclusion criteria

- (1) Concomitant organic gastrointestinal disease
- (2) Diagnosed or presenting with serious mental illness (e.g., eating disorder, schizophrenia, psychosis, obsessive-compulsive disorder, post-traumatic stress disorder, or a dissociative disorder)

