d. What is the frequency for review of summarized safety information and who will perform the review (e.g., safety monitoring board)?

- e. What are the stopping rules with regard to efficacy and safety?
Patients are free to withdraw from treatment at any time.

VIII. Analysis Plan

Aim 1: Feasibility and Acceptability of Treatment. Methods: Eligible and enrolled patients will be followed to assess the percentage who log-in to the web interface, utilize the materials sufficiently, complete the 12 week program, and report at least average satisfaction with treatment. We will present descriptive statistics to report treatment satisfaction and patient-reported global ratings of outcome, both of which will only be assessed at 12 weeks. Feasibility will be calculated as the proportion of participants who complete the FD HYP treatment program in comparison to those who drop out before treatment is completed. We expect that the proportion of participants who are retained will be 80%, demonstrating feasibility of recruitment and retention. Treatment satisfaction will be calculated as the proportion of patients who started treatment (dropouts included) who report that they are satisfied with the treatment (i.e., endorse the response either options “Somewhat satisfied”, “Very satisfied” or “Extremely satisfied” on the 7-point treatment satisfaction measure). We expect that the majority of patients will report satisfaction with the treatment. Sample size justification: For the aim of retention, a sample size of $n=23$ achieves 92.8% power for a one-sided exact test for a proportion retained of 80%. This test assumes the null hypothesis proportion retained is 50%, and we will reject the null hypothesis and conclude retention is acceptable should at least $n=16$ (69.6%) be retained. Similarly, for the aim of satisfaction, a sample size of 21 achieves 90.5% power for a one-sided exact test for a proportion satisfied of 50%. This assumes 20% satisfaction under the null hypothesis, and we will reject the null hypothesis if at least 39% of the sample report they are satisfied with treatment. Both tests were targeted at an $\alpha=0.05$ significance level.

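### The satisfaction test's 39% cut-off does not fit its n of 21 and 90.5% power: applied to 21 patients, the written rule has 80.8% power

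*Combined protocol and SAP*

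**What the plan says.** The combined protocol and SAP gives the satisfaction test in section VIII (Analysis Plan, Aim 1, sample size justification):

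- Size, power and alternative: "a sample size of 21 achieves 90.5% power for a one-sided exact test for a proportion satisfied of 50"%.
- Null: "This assumes 20% satisfaction under the null hypothesis".
- Decision rule: "we will reject the null hypothesis if at least 39% of the sample report they are satisfied with treatment".
- Significance level: 0.05, shared with the retention test.

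Earlier in the same section the endpoint is defined: "Treatment satisfaction will be calculated as the proportion of patients who started treatment (dropouts included"). Patients count as satisfied if they choose one of the top three options on the 7-point scale.

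Section V.c sets the enrolment: "We will enroll 23 adults with FD from the Loyola University Medical Center outpatient gastroenterology practices". It also says that the sample size was determined for Aim 1. Neither section says why the satisfaction test uses 21.

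**The concern.** The sample size, power and rejection rule of an exact binomial test are tied together. Once n and the null are fixed, the critical count follows, and the power follows from that count. Here the percentage cut-off does not correspond to the critical count that gives the stated power at the stated n.

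This sentence is the decision rule for acceptability, one half of the aim on which the study was sized. If 21 patients start and 8 report satisfaction, the planned exact test rejects the null (p = 0.043) but the written threshold is not met. The plan would then support either conclusion, and the choice would be made after the data were seen.

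**Working it through.** **Inputs**, all from section VIII, Aim 1, except enrolment (section V.c): null proportion 0.20; alternative 0.50; one-sided exact test; alpha 0.05; n = 21; stated power 90.5%; cut-off at least 39%; denominator all who started treatment; enrolment 23.

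**Formula.** For X ~ Binomial(n, p) and rejection when X ≥ r, alpha = P(X ≥ r | p = 0.20) and power = P(X ≥ r | p = 0.50). The exact critical count is the smallest r with alpha ≤ 0.05.

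**Step 1: reproduce the stated power.** At n = 21, r = 7 gives alpha 0.1085, which is too large. r = 8 gives alpha 0.0431 and power 0.9054. So the plan's 90.5% is correct for n = 21 with rejection at 8 or more. As a percentage, that cut-off is 8/21 = 38.1%.

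**Step 2: apply the written rule to 21 patients.** 0.39 × 21 = 8.19, so at least 9 must be satisfied (9/21 = 42.9%). Then alpha = 0.0144 and power = 0.8083. The loss is 90.5 − 80.8 = 9.7 points, which is the probability of exactly 8 of 21 when the true proportion is 50%.

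**Step 3: can rounding explain 39%?** No. 8/21 rounds to 38% and 9/21 to 43%, so no count out of 21 rounds to 39%.

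**Step 4: where 39% does fit.** At n = 23, r = 8 gives alpha 0.0715 (too large) and r = 9 gives alpha 0.0273 and power 0.8950. 9/23 = 39.1%.

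**Step 5: how far the conflict extends.** Exact critical count against the count needed to reach 39%:

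| Starters | Exact critical count | Count under 39% rule | Alpha, 39% rule | Power, exact test | Power, 39% rule |
|---|---|---|---|---|---|
| 20 | 8 | 8 | 0.0321 | 86.8% | 86.8% |
| 21 | 8 | 9 | 0.0144 | 90.5% | 80.8% |
| 22 | 9 | 9 | 0.0201 | 85.7% | 85.7% |
| 23 | 9 | 9 | 0.0273 | 89.5% | 89.5% |

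The two counts also agree at every n from 16 to 19. In the range 16 to 23, 21 is the only size at which they differ, and it is the size the plan names.

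**Step 6: compare the retention test.** That test is stated as a count with its n and percentage: 16 of 23 (69.6%), 92.8% power, null 50%, alternative 80%. It reproduces (alpha 0.0466, power 0.9285). The satisfaction test gives no count, and its percentage does not fit its n.

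**The case against.** The strongest reply accepts the arithmetic and disputes the weight.

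- **80.8% is the low point of a narrow case.** It applies only if the denominator is exactly 21. If all 23 start, the 39% rule is the exact rule and power is 89.5%, one point below the stated figure. This stands, and it limits the size of the problem.
- **The rules rarely disagree.** They differ only at 8 satisfied out of 21. Given 21 starters, that has probability 9.7% at 50% satisfaction and 2.9% at 20%. From 16 to 23 starters the written rule keeps alpha below 0.05, so it errs on the conservative side. This also stands.
- **21 may have a simple origin.** It is the smallest n with at least 90% exact power for 50% against 20%, just as 23 is the smallest for the retention test. The sentence may join the minimum n of one calculation to the cut-off for the enrolled n. That is plausible, but the plan does not say so, and it does not rescue the sentence: at 23 the power is 89.5%, not 90.5%. That 39% came from 9/23 is likewise an inference from the match.
- **This is a single-arm pilot.** Section V.d lists satisfaction among the secondary endpoints, and no go/no-go decision is tied to the test. That argues for moderate weight. It does not make a threshold and a power figure that contradict each other acceptable.

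**Conclusion.** The concern holds. The stated 90.5% power belongs to rejection at 8 of 21 (38.1%), and the stated rule of at least 39% excludes that result. Read literally at n = 21, the test has alpha 0.0144 and power 80.8%. At the planned enrolment of 23 the 39% rule is the correct exact rule, but its power is 89.5%.

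The figures assume the plan's own 20% and 50% proportions and an exact one-sided test at 0.05. The fall to 80.8% further assumes that exactly 21 patients start treatment. Type I error is not inflated. The point should be corrected because the rule is ambiguous at the very sample size the plan names.

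**What to change.** Replace the satisfaction sentence with one that gives a count and its denominator. For example: the test includes all patients who start treatment (planned n = 23), with dropouts counted as not satisfied; the null of 20% is rejected if 9 or more of 23 (39.1%) are satisfied; exact one-sided alpha is 0.027 and power is 89.5% at 50% satisfaction.

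A patient may enrol and never log on, so the number who start could be below 23. The sentence should therefore add that the exact critical count for the actual number of starters applies in place of a fixed percentage: 9 of 22, 8 of 21 or 8 of 20.

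The cost is one corrected sentence and one point of stated power (90.5% to 89.5%). Enrolment and study procedures do not change. If the sponsor prefers to keep 21 as the planned denominator, the cut-off must read 8 of 21 (38.1%), and the plan must explain why 21 of the 23 enrolled are expected to start.

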A published pilot study of hypnotherapy for IBS delivered entirely through audio recordings by co-investigator [name] and his colleagues serves as a model for the hypnosis treatment in this FD trial¹⁹. That study found that IBS patients who completed a seven-session self-administered audio home hypnosis treatment course were twice as likely (53% vs 26%) to have a reduction in their gastrointestinal symptoms by half or more at 6 months compared to matched control patients of the same age and sex and equal symptom severity who only received standard medical care. We will script the audio-recorded hypnosis protocol in the present trial to be similar in structure and therapy approach, as IBS and functional dyspepsia are both functional GI disorders and have many similarities and a high degree of overlap (the intervention tested in the prior hypnosis trial by Calvert et al., that showed high success in FD treatment, also utilized modified IBS hypnosis treatment for that purpose).

III. Study Aims

The purpose of this pilot study is to develop and test a hypnotherapy (HYP) treatment program for functional dyspepsia (FD) that can be self-administered using on-line audio recordings. We hypothesize that patients will be receptive to the self-administered treatment design and willing to participate and complete the 12-week treatment program.

Furthermore, we expect that patients will experience a significant reduction in FD symptoms following the intervention. Our specific aims include:

Aim 1: Feasibility and Acceptability of Treatment

The study will assess whether patients with FD will be willing to participate in the on-line treatment program and the majority of patients enrolled in the study will complete the 12 week program, utilize the materials sufficiently, and report average to above average satisfaction with treatment.

Aim 2: Treatment Effectiveness

The primary endpoint for Aim 2 is significant reduction in pre- to post- treatment FD symptom scores. Secondary endpoints include significant improvements in pre- to post-treatment score on psychological indices (e.g., anxiety) and disease-specific quality of life.

IV. Administrative Organization

All administrative activities related to the study will take place within the Division of Gastroenterology and Nutrition at Loyola University Medical Center (LUMC).

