Participants will have access to audio recordings of the protocol (pre-recorded by [name], study PI) via secure streaming online that will work on any computer or mobile device with internet access. Patients will be assigned a new hypnotherapy session to listen to every 2 weeks and these will become automatically available in the correct sequence. Each hypnotherapy session

will be approximately 30 mins in length. The hypnotherapy sessions are verbally guided exercises, similar to guided meditation. The hypnotherapy sessions encourage patients to enter a state of focused mental attention and deep physical relaxation during which images and verbal suggestions are used to positively influence emotional and physical symptoms. The session developed for this intervention will specifically focus on mechanisms that contribute to functional dyspepsia symptoms, such as impaired relaxation of the stomach and pain sensitivity. For example, after facilitating a deeply relaxed state patients will be asked to visualize drinking a cool liquid that has a therapeutic effect on the stomach (i.e., decreases pain, allows the stomach to stretch and make room for food). Each of the 7 sessions will utilize different imagery.

Patients will be instructed to practice a shorter 10-12 minute audio recording 5 times per week in between the longer sessions. After the 12-week treatment course is completed, patients will be able to continue to listen to the shorter home hypnosis recordings as often as they choose for up to one year.

The web page will give patients pop-up notices to encourage them to increase their frequency of practice if their weekly frequency drops below the recommended 5 days of home practice. Patients who do not log into the online system to complete a hypnosis exercise for 7 consecutive days will be contacted by the study coordinator to discuss whether the patient is interested in continuing with the trial.

Additionally, patients will receive phone or MyLoyola messaging (patient preference) from a study coordinator every 2 weeks to encourage adherence and troubleshoot any difficulty using the recordings and assess any adverse effects. If they have any difficulties or discomforts associated with the self-administered hypnosis intervention during the trial, they will have an opportunity to talk with [name] on the phone to resolve these.

The Study Website

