Aim 2: Treatment Effectiveness. Methods: The primary analyses to estimate treatment effects in this study will be linear mixed effects regression analysis. Mixed effects regression is flexible for modeling linear and nonlinear trends over time and robust to data missing at random. A separate mixed effects model will be specified for each of our primary outcome variables (DSSI and NDI-SF). Residual analysis will be performed and transformations of outcome measures will be applied as necessary. These models will estimate treatment effects at each follow-up time point controlling for baseline score. Secondary endpoints include significant improvements in pre- to post- treatment score on psychological indices (e.g., anxiety) and disease-specific quality of life. We will apply a similar approach using mixed effects regression analyses for these outcomes. Analyses will be performed using SAS 9.4 (SAS Institute, Cary, NC).

IX. Literature Cited

6. [name] OS. Hypnosis treatment of gastrointestinal disorders: A comprehensive review of the empirical evidence. *Am J Clin Hypn*. 2015;58(2):134-158.

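### Aim 2 rests on missing at random alone, with no commitment to collect symptom scores after a patient stops hypnosis and no sensitivity analysis

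*Combined protocol and SAP*

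**What the plan says.** **The contact after a lapse.** Section VI.c: "Patients who do not log into the online system to complete a hypnosis exercise for 7 consecutive days will be contacted by the study coordinator", the purpose being to "discuss whether the patient is interested in continuing with the trial". The section describes no separate choice to stop hypnosis but go on answering questionnaires. Under its Study Website heading, the questionnaire button appears inside the same portal as the audio player.

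**The endpoint and model.** Section III: "The primary endpoint for Aim 2 is significant reduction in pre- to post- treatment FD symptom scores". Section VIII, Aim 2, uses a linear mixed model: "These models will estimate treatment effects at each follow-up time point controlling for baseline score". Its only remark on missing scores is "Mixed effects regression is flexible for modeling linear and nonlinear trends over time and robust to data missing at random". It states no sensitivity analysis and no rule for scores after hypnosis stops.

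**Related provisions.**
- Section VI.d sets questionnaires at baseline, week 6, week 12 and 3 months after treatment. Patients are paid per assessment, with a larger sum at week 12.
- Section V.c allows up to 20% drop-out and wants at least 16 of 23 patients to complete through end of treatment, when the primary endpoint is measured.
- Section VIII, Aim 1, keeps drop-outs in the denominator for satisfaction. Aim 2 has no counterpart for symptom scores.

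**The concern.** Patients who feel no benefit have the most reason to stop listening. If the conversation prompted by a lapse is about the trial as a whole, some patients who would still have answered questionnaires may leave altogether. The shared portal adds to this, since a patient who no longer logs in for the audio does not see the questionnaire button.

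A model that assumes missing at random predicts the missing scores from patients with similar recorded scores who stayed. If the recorded scores do not capture why a patient left, the prediction is too favourable and the average reduction is overstated. The study has one arm, so there is no comparison group against which to judge this. At stake is the Aim 2 estimate, which the plan would report with nothing to show how far it depends on the assumption. The Aim 1 tests are not affected.

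**Working it through.** **Step 1. The plan's own figure.** Section VIII tests retention with n = 23, rejecting a null of 50% if at least 16 are retained, and states 92.8% power at 80% retention. The exact binomial calculation gives one-sided alpha 0.0466 and power 0.9285, so the figure reproduces. It supplies two drop-out fractions: d = 0.20 (expected) and d = 7/23 = 0.304 (the lowest retention the rule accepts).

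**Step 2. Size of a possible overstatement.** The documents give no effect size or standard deviation for Aim 2, so the inputs here are assumptions. Let g be the drop-outs' mean change as a share of the completers' mean change, and suppose that drop-outs supply no informative follow-up. The model then gives everyone roughly the completers' change, while the all-patient change is (1 − d) + d·g of it. The overstatement is 1/[(1 − d) + d·g] − 1.

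| g | d = 0.20 | d = 0.304 |
|---|---|---|
| 1 | 1/1.000 − 1 = 0% | 1/1.000 − 1 = 0% |
| 0.5 | 1/0.900 − 1 = 11% | 1/0.848 − 1 = 18% |
| 0.25 | 1/0.850 − 1 = 18% | 1/0.772 − 1 = 30% |
| 0 | 1/0.800 − 1 = 25% | 1/0.696 − 1 = 44% |

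The last row is the maximum provided that drop-outs do not get worse on average.

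**Step 3. What week 6 contributes.** The planned model can use a week-6 score where there is one. This was examined in a large-sample simulation (400,000 patients) of the missing-at-random estimate. Assumed inputs:
- between-patient variance 1 and measurement-error variance 0.3 at each visit;
- mean week-12 change −0.8, with between-patient standard deviation 0.6, half of it reached by week 6;
- drop-out logistic, with slope 1.5 per standard deviation of the driving variable.

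| Drop-out driven by | Week 6 observed (d = 0.20; 0.304) | Week 6 also missing (d = 0.20; 0.304) |
|---|---|---|
| Week-6 change | 0.1%; 0.1% | 14.3%; 20.8% |
| Patient's underlying benefit | 11.8%; 17.1% | 16.9%; 24.9% |
| Week-12 change | 19.2%; 28.4% | 25.9%; 38.2% |

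The assumption does its job when the observed week-6 change explains drop-out, and fails when the reason is unseen or week 6 is also missing. The 25.9% slightly exceeds the 25% of Step 2 because the simulated drop-outs worsen a little: their mean change is [−0.802 − 0.80 × (−1.024)]/0.20 = +0.086.

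**The case against.** The strongest reply is that the plan contains no rule that discards data. A reader might infer from Section VI.c that patients who lapse lose their remaining assessments. The text does not say so. Seven days without a log-in is a lapse, not proof of stopping, and the coordinator only asks a question. Staff monitor questionnaire completion separately from session completion and send reminders (Section VI.c). Payment in Section VI.d is not tied to hypnosis use. Section VII speaks in places of stopping treatment and in others of leaving the study. All of this stands. It means that collection after stopping is left open, not that it is excluded. It does not supply the missing commitment.

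The upper figures are also extreme, for three reasons:
- They describe drop-outs with no change and no informative follow-up, whereas the model can use week 6.
- Zero change fits poorly with the protocol's own background: 34% and 43% of control patients improved in the earlier dyspepsia trial, and 26% of standard-care patients in the IBS pilot had symptoms fall by half or more.
- Sixteen of 23 is a test threshold, not the expected retention of 80%, and it counts completion of treatment rather than returned questionnaires.

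These points stand, and they are why the size is given as a range starting at zero.

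A reader might also convert the overstatement into lost power for the later randomized trial. The documents do not support that step. Section V.c says the pilot data will serve to power such a trial, but it does not name the pre-to-post change as the planning effect. A two-arm trial is powered on a between-arm difference, which a single-arm change cannot supply even with complete data.

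**Conclusion.** The point holds as a gap that is cheap to close. The plan turns a lapse in hypnosis into a question about continuing with the trial, does not commit to scores after hypnosis stops, and relies on missing at random with no check.

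Whether the Aim 2 reduction is overstated depends on why patients leave, which the documents cannot show. Where drop-outs give no informative follow-up, the overstatement runs from 0% (they improve like completers) through 11% to 18% (half the benefit) to 25% at 20% drop-out or 44% at 16 of 23 retained (no change). It is about 0% if observed week-6 scores explain drop-out. With 23 patients the data cannot settle which case applies, and that is the reason for a sensitivity analysis.

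**What to change.** 1. **Section VI.c.** Have the coordinator ask about stopping hypnosis and stopping questionnaires as two separate questions. Keep sending the week 6, week 12 and 3-month questionnaires to patients who stop hypnosis, with the same payment and reminders. State in Section VIII that these scores enter the Aim 2 model. This step matters most, because scores not collected during the study cannot be recovered.

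2. **Section VIII, Aim 2.** Prespecify one sensitivity analysis for the primary symptom score. Impute missing post-treatment scores around the patient's own baseline and report the result beside the mixed-model estimate, labelled as a conservative bound. First settle which score is meant: Section VI.d lists the PAGI-SYM, while Section VIII names the DSSI, which is not among the listed questionnaires.

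The cost is protocol wording, a few extra reminders and one more analysis; gift certificates are already planned per assessment. The downside is that the sensitivity estimate may understate benefit, since some drop-outs will have improved. The intervention, the sample size and the Aim 1 tests stay as they are.
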